
 To further describe the immune response induced by MenABCWY, as measured by hSBA performed with ACWY and 4 primary MnB test strains, 1 month after a booster vaccination in Groups 1 and 3. 	
 Proportions of subjects with hSBA-MenA, hSBA-MenC, hSBA-MenW, and hSBA-MenY titers $\geq 1:8$, $\geq 1:16$, $\geq 1:32$, $\geq 1:64$, and $\geq 1:128$ at Visit 11, in Groups 1 and 3 separately. hSBA GMTs for each of the ACWY test strains at Visit 11, in Groups 1 and 3 separately. Proportion of subjects who achieve the 5 MnB endpoints at Visit 11, in Groups 1 and 3 combined. Proportions of subjects with hSBA titers $\geq 1:4$, $\geq 1:8$, $\geq 1:16$, $\geq 1:32$, $\geq 1:64$, and $\geq 1:128$ for each of the 4 primary MenB test strains at Visit 11, in Groups 1 and 3 combined. hSBA GMTs for each of the 4 primary MnB test strains at Visit 11, in Groups 1 and 3 combined.

 To further describe the immune response induced by bivalent rLP2086, as measured by hSBA performed with 4 primary MnB test strains, 2 expressing an LP2086 subfamily A protein and 2 expressing an LP2086 subfamily B protein, measured 1 month after the booster vaccination in Groups 2 and 4. 	
 Proportion of subjects who achieve the 5 MnB endpoints 1 month after the booster vaccination, in Groups 2 and 4 combined. Proportions of subjects with hSBA titers $\geq 1:4$, $\geq 1:8$, $\geq 1:16$, $\geq 1:32$, $\geq 1:64$, and $\geq 1:128$ for each of the 4 primary MenB test strains at Visit 11, in Groups 2 and 4 combined. hSBA GMTs for each of the 4 primary MnB test strains at Visit 11, in Groups 2 and 4 combined.

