MenABCWY (Groups 1 and 3 combined in Stage 2)	1 Month after the booster dose of MenABCWY (Visit 11)	PMB80 (A22), PMB2001 (A56), PMB2948 (B24), PMB2707 (B44)	Composite response (proportion of subjects achieving an hSBA titer \geq LLOQ for all 4 MnB strains) Proportion of subjects achieving at least a 4-fold increase in hSBA titer from baseline for each of the 4 MnB strains Proportion of subjects with hSBA titer \geq 1:4, \geq 1:8, \geq 1:16, \geq 1:32, \geq 1:64, \geq 1:128 for each MnB strain hSBA GMTs for each MnB strain
MenABCWY (Groups 1 and 3 separately in Stage 2)	1 Month after the booster dose of MenABCWY (Visit 11)	hSBA-MenA, hSBA-MenC, hSBA-MenW, hSBA-MenY	Proportion of subjects with hSBA-MenA/C/W/Y titer \geq 1:8, \geq 1:16, \geq 1:32, \geq 1:64, \geq 1:128 hSBA-MenA/C/W/Y GMTs
Bivalent rLP2086 + MenACWY-CRM (Groups 2 and 4 combined in Stage 2)	1 Month after the booster dose of bivalent rLP2086 + MenACWY-CRM (Visit 11)	PMB80 (A22), PMB2001 (A56), PMB2948 (B24), PMB2707 (B44)	Composite response (proportion of subjects achieving an hSBA titer \geq LLOQ for all 4 strains) Proportion of subjects achieving at least a 4-fold increase in hSBA titer from baseline for each of the 4 strains Proportion of subjects with hSBA titer \geq 1:4, \geq 1:8, \geq 1:16, \geq 1:32, \geq 1:64, \geq 1:128 for each strain hSBA GMTs for each strain

Abbreviations: GMT = geometric mean titer; hSBA = serum bactericidal assay using human complement; LLOQ = lower level of quantitation; MenA, MenB, MenC, MenW, and MenY = *Neisseria meningitidis* groups A, B, C, W, and Y; MnB = *Neisseria meningitidis* group B.

The exploratory analysis to investigate the association of the primary strains and additional MenB testing strains, as well as a sensitivity analysis that may be performed for immunogenicity in Stage 1, will be detailed in the SAP.

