**Table 1. Summary of Major Changes in SAP Amendments**

Version / Date	Associated Protocol Amendment	Rationale	Specific Changes
4 17MAY2021	Amendment 2, 09JUL2019	Protocol Amendment	
 
• Moved the booster dose safety endpoints from secondary to primary safety endpoints.
 
• Moved some immunogenicity endpoints (related to persistence evaluation) from secondary to exploratory endpoints.
 
• Removed the 1:4 endpoint for ACWY strains for the persistence and booster endpoints.
 
• Updated the Stage 2 enrollment, for ACWY-experienced subjects in addition to ACWY-naïve subjects to obtain data on the persistence of the immune response after 2 doses of Neisseria meningitidis group A, B, C, W, and Y vaccine (MenABCWY) as well as on the safety and immunogenicity of the booster response in individuals who had previously received an ACWY-containing vaccine.
 
• Removed the persistence and booster endpoints for defined titers; removed the persistence endpoints for geometric mean titers (GMTs).
 

5 28 Feb 2022	N/A	
Table reduction initiative, including reducing redundancy
 
Adding additional analyses
 
Administrative changes
	
 
• Removed from Stage 2 analyses the exploratory 4-fold rise and the composite response endpoint for MenB strains.
 
• Replaced some study conduct tables for Stage 2 with listings in Section 6.6.
 
• Added exploratory analyses for MenA/C/W/Y to investigate the relationship between the pre-booster dose and the post-booster dose titers in Section 6.4.
 
• Added in Section 7.1 a new planned reporting event performed when subjects have completed the 1-month postbooster blood draw.
 
• Updated the temperature scale of severity for fever for Stage 2 (Table 14) in Section 3.5.2.2 to allow for consistency in severity designation between temperatures recorded in Fahrenheit and Celsius.
 
• Added the definition of the booster safety population in Section 4.4.
 

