- Proportions of subjects with hSBA titers  $\geq$  LLOQ,  $\geq 1:4$ ,  $\geq 1:8$ ,  $\geq 1:16$ ,  $\geq 1:32$ ,  $\geq 1:64$ , and  $\geq 1:128$  for each of the 4 primary MenB test strains at Visits 1 and 3, in the ACWY-naïve and ACWY-experienced subjects combined.
- hSBA GMTs for each of the 4 primary MenB test strains at Visits 1 and 3, in the ACWY-naïve and ACWY-experienced subjects combined.

Immune response induced by MenABCWY compared to MenACWY-CRM and bivalent rLP2086 at blood sampling time points prior to the booster vaccination (Stage 2).

- Proportions of subjects with hSBA-MenA, hSBA-MenC, hSBA-MenW, and hSBA-MenY titers  $\geq 1:8$  (or LLOQ, whichever is higher) at Visits 7, 8, 9, and 10, in the ACWY-naïve and ACWY-experienced subjects separately.

- Proportions of subjects with hSBA titers  $\geq$  LLOQ for each of the 4 primary MenB test strains at Visits 7, 8, 9, and 10, in the ACWY-naïve and ACWY-experienced subjects combined.

Immune response induced by MenABCWY 1 month after a booster vaccination in Groups 1 and 3.

- Proportions of subjects with hSBA-MenA, hSBA-MenC, hSBA-MenW, and hSBA-MenY titers  $\geq$ 1:8 (or LLOQ, whichever is higher) at Visit 11 in Groups 1 and 3 separately.
- Proportions of subjects with hSBA titers  $\geq$  LLOQ for each of the 4 primary MenB test strains at Visit 11 in Groups 1 and 3 combined.

Immune response induced by bivalent rLP2086 measured 1 month after the booster vaccination in Groups 2 and 4.

- Proportions of subjects with hSBA titers  $\geq$  LLOQ for each of the 4 primary MenB test strains at Visit 11 in Groups 2 and 4 combined.

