The endpoints related to the exploratory objective to further describe the immune response induced by MenABCWY compared to the immune response induced by MenACWY-CRM and bivalent rLP2086, as measured by hSBA performed with ACWY test strains and 4 primary MenB test strains, 2 expressing an LP2086 subfamily A protein and 2 expressing an LP2086 subfamily B protein at blood sampling time points prior to the booster vaccination (Stage 2), are not planned to be reported.

Furthermore, for the last 2 exploratory objectives related to the further description of the immune response following the booster vaccination, the endpoints related to the proportion of subjects with titers  $\geq 1:4$ ,  $\geq 1:8$ ,  $\geq 1:16$ ,  $\geq 1:32$ ,  $\geq 1:64$ , and  $\geq 1:128$  and the endpoints related to the proportion of subjects who achieve the 5 MenB endpoints are not planned to be reported.

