### 5.2.1.2. Immunogenicity Data

Each primary MenB strain has a validated LLOQ value defined, and each secondary MenB strain and each ACWY serogroup has a qualified LLOQ (Table 16).

**Table 16. Validated hSBA LOD and LLOQs for Primary MenB Strains and Qualified LLOQs and LODs for Secondary MenB Strains and ACWY Assays**

Strain/Serogroup Type	Strain Variant/Serogroup	LOD	LLOQ
Primary MenB	A22	1:4	1:16
	A56	1:4	1:8
	B24	1:4	1:8
	B44	1:4	1:8
Secondary MenB	A29	1:4	1:8
	A06	1:4	1:16
	A12	1:4	1:16
	A07	1:4	1:8
	A15	1:4	1:8
	A19	1:4	1:16
	B16	1:4	1:8
	B09	1:4	1:8
	B03	1:4	1:8
	B15	1:4	1:8

**Table 16. Validated hSBA LOD and LLOQs for Primary MenB Strains and Qualified LLOQs and LODs for Secondary MenB Strains and ACWY Assays**

Strain/Serogroup Type	Strain Variant/Serogroup	LOD	LLOQ
ACWY	MenA	1:4	1:8
	MenC	1:4	1:8
	MenW	1:4	1:8
	MenY	1:4	1:8

Abbreviations: ACWY = *Neisseria meningitidis* group A, C, W, Y; hSBA = serum bactericidal assay using human complement; LLOQ = lower limit of quantitation; MenB = *Neisseria meningitidis* serogroup B.

All hSBA titers assessed for either MenB or MenA/C/W/Y will be analyzed as follows. At each visit where assay titers are analysed (Visits 1, 2, 3, 4, 7, 8, 9, 10, and 11), subjects with hSBA titers  $\geq$  LLOQ will be derived as follows:

- = ●, if the assay result is missing, indeterminate, or otherwise unavailable;
- = 1, if the assay result meets the specific LLOQ value;
- = 0, if the assay result does not meet the specific LLOQ value.

Similarly for all hSBA titers assessed, binary variables of assay results at each visit where assay titers are analyzed and who achieve a specific threshold ( $\geq 1:4$ ,  $\geq 1:8$ ,  $\geq 1:16$ ,  $\geq 1:32$ ,  $\geq 1:64$ , and  $\geq 1:128$ ) will also be derived.

- = ●, if the assay result is missing, indeterminate, or otherwise unavailable;
- = 1, if the assay result meets the specific threshold value;
- = 0, if the assay result does not meet the specific threshold value.

A composite response will be computed for Stage 1, 1 month after the second vaccination (Visit 4). The composite response is defined as subjects who have assay results that are  $\geq$  LLOQ for all 4 of the primary MenB strains at the same visit.

- = ●, if the assay result is missing, indeterminate, or otherwise unavailable for at least 1 of the 4 MenB primary strains;
- = 1, if all 4 MenB primary strains have assay results  $\geq$  LLOQ at the same visit;

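### SAP version 5 drops the protocol's exploratory 4-strain MenB composite after the booster, and the per-strain results it keeps do not determine it

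*Protocol*

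**What the plan says.** **Protocol.** Section 2 lists two exploratory entries one month after the booster: "Proportion of subjects who achieve the 5 MnB endpoints at Visit 11, in Groups 1 and 3 combined" and "Proportion of subjects who achieve the 5 MnB endpoints 1 month after the booster vaccination, in Groups 2 and 4 combined". The five endpoints are a 4-fold rise for each of the four primary strains, plus the composite. Table 17 in section 9.2.3 names the composite at Visit 11 for both combined arms; for the MenABCWY arms it requires a titer at or above "LLOQ for all 4 MnB strains".

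**SAP.** Table 1, version 5, records the change: "Removed from Stage 2 analyses the exploratory 4-fold rise and the composite response endpoint for MenB strains". The rationale column reads "Table reduction initiative, including reducing redundancy", and it covers several changes at once. Section 3.3.1 still tabulates the endpoints but then says that "the endpoints related to the proportion of subjects who achieve the 5 MenB endpoints are not planned to be reported"; section 2.1.5 says the same. Section 5.2.1.2 ties the derivation to one visit: "A composite response will be computed for Stage 1, 1 month after the second vaccination (Visit 4").

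**What remains for MenB after the booster.** The secondary endpoint is the proportion at or above "LLOQ for each of the 4 primary MenB test strains at Visit 11 in Groups 1 and 3 combined", with a parallel entry for Groups 2 and 4. SAP Tables 18 and 19 show it at Visits 4, 10 and 11. Tables 20 and 21 add per-strain GMTs at the same visits. Reverse cumulative distribution curves are optional (SAP 6.2.1.2).

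**The concern.** The composite is a coprimary endpoint after the second dose, and it is the only one of the five that counts breadth of response within a subject. The SAP reports it after dose 2 (Table 17) and, as an exploratory result, after dose 1 (Table 20). It is then missing after the booster, where the protocol also lists it.

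A table can safely be cut as redundant if a reader could rebuild it from the tables that stay. Four separate strain percentages cannot be turned into the share of subjects who respond to all four strains, and neither can four GMTs. At stake is a descriptive statement: what proportion of boosted subjects meet the trial's own 4-strain standard, and how that compares with one month after dose 2 in the same subjects.

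**Working it through.** **Step 1: the plan's own composite figure.** The documents give no figure for the composite after the booster. The nearest is protocol Table 12: an assumed composite of 72.9% after two doses, a criterion of 65%, 900 evaluable subjects and power of 99.92%. The smallest count whose Clopper-Pearson lower limit exceeds 65% is 614 of 900, and P(X ≥ 614 | n = 900, p = 0.729) = 0.9992. The product of the five powers is 0.952. Both agree with the table. The 72.9% serves below only as a reference point.

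**Step 2: what four percentages imply.** With per-strain proportions p1 to p4, the composite C satisfies

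max(0, p1 + p2 + p3 + p4 − 3) ≤ C ≤ min(p1, p2, p3, p4).

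For a common rate p the bounds are max(0, 4p − 3) and p. The rates are assumptions, because the documents give no post-booster rates. To show what is plausible inside the bounds, the table also gives C under an equicorrelated latent-normal model. At zero correlation C is p to the fourth power.

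| Rate per strain | Extreme bounds | Corr. 0 | 0.3 | 0.6 | 0.9 |
|---|---|---|---|---|---|
| 85% | 40% to 85% | 52.2% | 59.3% | 66.9% | 76.7% |
| 90% | 60% to 90% | 65.6% | 70.5% | 76.1% | 83.7% |
| 95% | 80% to 95% | 81.5% | 83.6% | 86.7% | 91.2% |

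At 90% per strain, the same four percentages fit a composite below or above 72.9%, depending only on how responses overlap within subjects.

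**Step 3: where the ambiguity fades.** The lower bound alone reaches 72.9% when p1 + p2 + p3 + p4 ≥ 3.729, an average of 3.729 / 4 = 93.2%. At 98% per strain the bounds are 92% to 98%.

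**Step 4: comparison with sampling error.** Exact 95% intervals at the planned Stage 2 sizes, before attrition:

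- Groups 1+3 (264): 192/264 gives 66.9% to 78.0%; 238/264 gives 85.9% to 93.5%.
- Groups 2+4 (130): 95/130 gives 64.6% to 80.5%; 117/130 gives 83.5% to 94.6%.

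At 90% per strain, the spread over correlations 0 to 0.9 is 83.7 − 65.6 = 18.1 points. The intervals around a composite near 72.9% are 11.1 and 15.9 points wide, so the omission costs more than sampling error. At 95% per strain the spread is 91.2 − 81.5 = 9.7 points, against intervals of 7.6 and 11.1 points around 90%, so the two are comparable.

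**Step 5: can it be computed?** All four strains are analysed at Visits 4 and 11 in the booster evaluable population (SAP Tables 18 and 19), and the Stage 1 rule already exists. That rule has to be widened in any case, since Table 20 uses the composite at Visit 2 while section 5.2.1.2 mentions only Visit 4.

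**The case against.** The endpoint is exploratory. Protocol section 9 allows the SAP to depart from the protocol where appropriate and requires an amendment only for major changes to the primary endpoints or their analyses. The removal is stated openly in three places, and the secondary booster measure, per-strain response at the LLOQ, is kept in full. All of this stands. The change is a disclosed reporting choice, not an undeclared deviation.

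The extreme lower bounds are also unlikely. At 90% or 95% per strain, they require that no subject misses more than one strain, which is hard to defend for four titers from one serum. The correlation range is therefore the fairer guide. Protocol section 1.2.2.1 reports that titers after a booster in an earlier study exceeded those after the primary series, so rates near the ceiling, where little ambiguity remains, are plausible.

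The SAP also does not say in terms that the composite itself is redundant, since the rationale is shared across several changes. That is correct, but whichever reason was meant, the retained tables do not contain the information.

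A reader might infer that the endpoint was removed because of what the data showed, since version 5 postdates Stage 1 reporting and Stage 2 is open-label. The documents do not support this: nothing shows that Visit 11 MenB results had been seen.

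A reader might also infer that a pre-booster composite was dropped. It was not: for Visits 7 to 10 the protocol lists only per-strain proportions and GMTs.

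**Conclusion.** The point holds as a low-cost improvement to the Stage 2 reporting. A composite that the protocol lists at Visit 11 has been dropped, and the retained per-strain percentages and GMTs do not determine it. If each strain is at 90%, the undetermined range is about 66% to 84% for latent correlations 0 to 0.9. It narrows to about 82% to 91% at 95% per strain, and to at most 6 points at 98%. These sizes rest on equal assumed rates across strains and on the latent-normal model; the bounds themselves need no model.

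It would go too far to say that the trial cannot describe the booster response in MenB: per-strain results are kept at Visits 4, 10 and 11, and strain rates averaging at least 93.2% would by themselves guarantee a composite of 72.9%. The primary objective, its power and the Stage 2 secondary endpoints are untouched.

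**What to change.** - In SAP 2.1.5 and 3.3.1, take the composite out of the list of endpoints that will not be reported.
- In the booster rows of Table 20 (Groups 2+4) and Table 21 (Groups 1+3), add the composite at Visits 4 and 11 in the booster evaluable population, with exact 95% confidence intervals. Visit 4 is needed in this population so that the comparison is made in the same subjects.
- In SAP 5.2.1.2, extend the composite derivation beyond Visit 4 to Visit 11, and to Visit 2, where Table 20 already uses it.

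A Visit 10 value would be a useful option, but it is an addition that the protocol does not list. The 4-fold rise and titer-threshold tables after the booster can stay dropped. The cost is one extra table from titers already measured, with no new samples or assays.

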3. STUDY DESIGN

This is a Phase 3, randomized, active-controlled, observer-blinded multicenter trial in which approximately 1590 subjects will be randomly assigned to receive either MenABCWY and placebo, or bivalent rLP2086 and MenACWY-CRM. All subjects will be naive to any meningococcal group B vaccine prior to enrollment.

Randomization will be stratified by prior vaccination history; approximately 795 ACWY-naive subjects and 795 ACWY-experienced (having received 1 prior dose of a vaccine containing 1 or more ACWY groups ≥ 4 years prior to the date of randomization) subjects will be enrolled.

Randomization will also be stratified by geographic region. Approximately 1320 subjects from US investigative sites and 270 subjects from ex-US countries will be randomized. Regional stratification will ensure sufficient population representation.

Enrollment targets will also be adjusted to achieve appropriate representation by age (subjects 10 to <18 years old and subjects 18 to <26 years old), age within ACWY strata, and ACWY strata within a geographic region. Additional details will be provided during pretrial assessment and site initiation visits.

The study will be conducted in 2 stages:

- Stage 1: from study entry (Visit 1) through Visit 6. See Table 1. A pilot cohort consisting of 10 subjects 18 to <26 years of age will first be enrolled at selected site(s). These pilot cohort subjects will be assigned to either Group 1 or 3, and therefore will receive MenABCWY at Vaccination 1. The sponsor will be unblinded to vaccine assignment for the pilot cohort. Seven (7) days after the last pilot cohort subject has received MenABCWY, 7-day electronic diary (e-diary) and AE data will be summarized for review by the sponsor’s independent review committee (IRC). No further enrollment will be permitted until review of these safety data is complete. If the IRC finds the safety data from the pilot cohort acceptable, enrollment will be opened to all ages and randomization groups, and pilot cohort subjects will proceed through the study. During Stage 1, the sponsor will be blinded to vaccine assignment beyond completion of pilot cohort enrollment (Section 5.4).

In order to support assay development, a subset of up to approximately 600 subjects 18 to 25 years of age will have up to 100 mL, rather than 20 mL, of blood drawn at Visits 1, 2, and 4; and a subset of up to approximately 150 subjects 18 to 25 years of age will have up to 100 mL, rather than 20 mL, of blood drawn at Visit 11. Subject participation in this subset will be voluntary, and the volume of blood drawn will depend on the consent obtained. Stage 1 will be observer-blinded.

At designated sites, an additional optional whole blood sample of approximately 50 mL will be obtained at Visit 4 from up to approximately 30 subjects 18 to 25 years of age. This sample will be used for exploratory purposes.

- Stage 2: from Months 18 to 60 (Visits 7 to 12). Subjects from both the ACWY-naïve and ACWY-experienced strata, approximately 132 from each of Groups 1 and 3 and approximately 65 from each of Groups 2 and 4, will participate in Stage 2. Stage 1 will be observer-blinded and Stage 2 will be open-label.

Table 1. Stage 1 Study Design

		Vaccination 1	Post-Vaccination 1 Blood Draw	Vaccination 2	Post-Vaccination 2 Blood Draw	Safety Telephone Call	Telephone Call
	Approximate Month	0	1	6	7	12	
	Visit Number	1	2	3	4	5	6
ACWY-Naive Subjects	Group 1 ^a (n=265)	MenABCWY + saline		MenABCWY			
	Group 2 (n=530)	Bivalent rLP2086 + MenACWY-CRM		Bivalent rLP2086			
	Blood Draw for serum collection	20 mL (or up to 100 mL in subset)	20 mL (or up to 100 mL in subset)	20 mL	20 mL (or up to 100 mL in subset)		

Table 1. Stage 1 Study Design

		Vaccination 1	Post-Vaccination 1 Blood Draw	Vaccination 2	Post-Vaccination 2 Blood Draw	Safety Telephone Call	Telephone Call
ACWY-Experienced Subjects	Group 3 ^a (n=265)	MenACWY + saline		MenACWY			
	Group 4 (n=530)	Bivalent rLP2086 + MenACWY-CRM		Bivalent rLP2086			
	Blood Draw for Serum Collection	20 mL (up to 100 mL in subset)	20 mL (up to 100 mL in subset)	20 mL	20 mL (up to 100 mL in subset)		
Subjects 18 to 25 years of age (naïve or experienced)	Optional Blood Draw for Whole Blood Collection				50 mL		

a. Pilot cohort subjects will be assigned to either Group 1 or 3, but will receive only MenACWY at Vaccination 1. Pilot cohort subjects will not receive saline at Vaccination 1.

Table 2. Stage 2 Study Design

		Antibody Persistence	Booster Vaccination	Postbooster Blood Draw	Safety Telephone Call
	Approximate Month	18-42	54	55	60
	Visit Number	7-9	10	11	12
ACWY-Naive Subjects	Group 1 (n ~132)		MenACWY		
	Group 2 (n ~65)		Bivalent rLP2086 + MenACWY-CRM		

Table 2. Stage 2 Study Design

		Antibody Persistence	Booster Vaccination	Postbooster Blood Draw	Safety Telephone Call
	Approximate Month	18-42	54	55	60
	Visit Number	7-9	10	11	12
ACWY-Experienced Subjects	Group 3 (n ~132)		MenABCWY		
	Group 4 (n ~65)		Bivalent rLP2086 + MenACWY-CRM		
	Blood Draw for Serum Collection	20 mL × 3	20 mL	20 mL (or up to 100 mL in subset)	

In Stage 2, the total number subjects for Groups 1 and 3 combined will be approximately 264 and the total number of subjects for Groups 2 and 4 combined will be approximately 130.

